- If 3 or more DLTs are observed in the initial 6 subjects, enrollment into Cohort 1 will be stopped and the dose will be de-escalated to Cohorts -1A and -1B.

A similar 6+3 cohort design will be utilized in the dose de-escalation cohorts. If necessary, the dose de-escalation cohort -2 will be enrolled thereafter.

If a subject experiences a DLT during the DLT observation period, the subject will discontinue treatment. However, any subject(s) tolerating the dose level through the DLT observation period will continue with the same dose level of study drug even if subsequently-enrolled study subjects receive treatment at a dose de-escalation.

A Dose Level Review Committee (DLRC) will evaluate the safety data from each cohort of Phase 1b. Members of this committee will include participating investigators or designees as well as the Sponsor (invitees include: the Medical Monitor or designee, the clinical lead, a Drug Safety representative and a Biostatistician) (see Section 12.11).

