5.3 Definition of Dose-Limiting Toxicity (DLT)

The assessment of DLT will follow the guidelines provided in the Common Terminology Criteria for Adverse Events (CTCAE) version 4.03 (accessible at the website, http://evs.nci.nih.gov/ftp1/CTCAE/CTCAE_4.03_2010-06-14_QuickReference_8.5x11.pdf). The Phase 1b DLT observation period will occur from Day 1 of Cycle 1 of ibrutinib in combination with MEDI4736 treatment to the laboratory evaluations on Day 1 of Cycle 2 which will occur before the MEDI4736 infusion on Day 1 of Cycle 2.

A DLT is an AE at least possibly related to study drug(s) defined as:

- 1) Any Grade 3 or higher non-hematologic AE (with additional clarifications below)
 - Grade 3 or higher nausea, vomiting, or diarrhea (non-colitis-related) that is uncontrolled by maximal supportive care and persists for >7 days would be considered a DLT
 - Grade 3 fatigue that persists for >7 days would be considered a DLT
 - Any Grade 3 immune-related adverse event (irAE) that does not downgrade to Grade ≤2 within 3 days after onset of the event despite maximal supportive care including systemic corticosteroids, or does not downgrade to Grade ≤1 or baseline within 14 days would be considered a DLT

- Any Grade ≥ 2 pneumonitis that does not resolve to Grade ≤ 1 within 3 days of the initiation of maximal supportive care would be considered a DLT.
- The DLT definition excludes the following conditions:
 - Grade 3 endocrinopathy that is managed with or without systemic corticosteroid therapy and/or hormone replacement therapy and the subject is asymptomatic
 - Grade 3 inflammatory reaction attributed to a local antitumor response (eg, inflammatory reaction at sites of metastatic disease, lymph nodes, etc)
 - Vitiligo or alopecia of any AE grade would not be considered a DLT
- 2) Clinically relevant hematologic AE such as:
 - Grade 3 or 4 neutropenia (ANC<1,000/ mm³) lasting >7 days
 - Febrile neutropenia (Grade 3 or 4 neutropenia with fever \geq 38.3°C)
 - Grade 3 or 4 thrombocytopenia (<25,000/ mm³) lasting >7 days or requiring transfusion or associated with Grade ≥2 bleeding
 - Any other Grade 4 hematologic AE, except lymphopenia

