5.6.1.4. Dose Modification for Adverse Reactions

For an ibrutinib-related adverse reaction, the dose of ibrutinib should be modified according to the dose modification guidelines in Table 3 if any of the following toxicities occur:

- Grade 4 neutropenia (ANC $<500/\mu$ L) for more than 7 days. See Section 6.1 and 6.3 for instructions regarding the use of growth factor support.
- Grade 3 thrombocytopenia (platelet count <50,000/mm³ (50 x 10⁹/L) in the presence of grade 2 or greater bleeding events.

- Grade 4 thrombocytopenia (platelet count $<25,000/\text{mm}^3$ (25 x $10^9/\text{L}$).
- Grade 3 or 4 nausea, vomiting, or diarrhea if persistent, despite optimal anti-emetic and/or anti-diarrheal therapy.
- Any other Grade 4 or unmanageable Grade 3 toxicity.

For Grade 3 or 4 atrial fibrillation or persistent atrial fibrillation of any grade, consider the risks and benefits of ibrutinib treatment. If clinically indicated, the use of anti-coagulants or anti-platelet agents may be considered for the thromboprophylaxis of atrial fibrillation (Section 6.2.3).

 Table 3.
 Ibrutinib Dose Modifications

Occurrence	Action to be Taken
First	Withhold study drug until recovery to Grade ≤ 1 or baseline; may restart at original dose level
Second	Withhold study drug until recovery to Grade ≤1 or baseline; may restart at 1 dose level lower (ie, 420 mg/day for original 560 mg/day dose; 280 mg/day for original 420 mg/day dose)
Third	Withhold study drug until recovery to Grade ≤1 or baseline; may restart at 1 dose level lower (ie, 280 mg/day for original 560 mg/day dose) or discontinue for original 420 mg/day dose
Fourth	Discontinue study drug

After a dose reduction, dose escalations of ibrutinib to the previous higher dose may be considered after consultation with the Medical Monitor if the event does not recur after at least one cycle of the lower dose.

If tumor lysis syndrome is diagnosed, follow the institutional guidelines for management.

Study treatment should be discontinued in the event of an ibrutinib toxicity lasting more than 28 days, unless reviewed and approved by the Medical Monitor.

Study treatment interruptions, dose reductions or modifications, or any other changes in study drug administration should be recorded in the clinical database.

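### The platelet DLT criterion names Grade 3 or 4 but prints the Grade 4 cut-off (<25,000/mm³), so qualifying counts of 25,000 to <50,000 are DLTs by the label and not by the number

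*Protocol*

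**What the plan says.** Section 5.3 lists the platelet criterion as "Grade 3 or 4 thrombocytopenia (<25,000/ mm³) lasting >7 days or requiring transfusion", with Grade 2 or higher bleeding as a third qualifier. The synopsis and SAP Section 1.1 carry the same grades and the same number.

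For ibrutinib dose modification, Section 5.6.1.4 gives "Grade 3 thrombocytopenia (platelet count <50,000/mm³" as the Grade 3 limit. Its next platelet line, "Grade 4 thrombocytopenia (platelet count", carries the limit <25,000/mm³.

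Three other parts of Section 5.3 bear on the reading:

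- "The assessment of DLT will follow the guidelines provided in the Common Terminology Criteria for Adverse Events (CTCAE) version 4.03".
- The hematologic list opens with "Clinically relevant hematologic AE such as", so it gives examples and is not closed.
- The neutropenia line reads "Grade 3 or 4 neutropenia (ANC<1,000/ mm³) lasting >7 days". Section 5.6.1.4 gives <500/µL on its line for "Grade 4 neutropenia (ANC".

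The last hematologic line in Section 5.3 covers other Grade 4 events only. Section 5.2 adds a consequence for the subject: "If a subject experiences a DLT during the DLT observation period, the subject will discontinue treatment".

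**The concern.** The label and the number in one criterion select different subjects, and no text says which governs. The 6+3 rule acts on a count of DLTs, so the definition has to give the same count whoever applies it.

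Two things depend on that count. The first is the dose decision: accept, add three subjects, or move to Cohorts -1A and -1B. The second is the management of the subject, who discontinues treatment if the event is a DLT and may continue if it is not.

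The replacement rule can hide the event as well. Drug may be withheld for a related Grade 3 platelet count with Grade 2 or higher bleeding (Section 5.6.1.4) or for a Grade 3 MEDI4736-related reaction (Table 4). If that leads to enough missed doses, and the event is not called a DLT, Section 5.4 replaces the subject and leaves them out of the DLT analysis.

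**Working it through.** **1. Label against number.** The grade limits are those printed in Section 5.6.1.4.

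| Item in Section 5.3 | Label | Number in 5.3 | Grade limits in 5.6.1.4 | Does the number cover Grade 3? |
|---|---|---|---|---|
| Neutropenia | Grade 3 or 4 | ANC <1,000 | Grade 4: <500 | Yes; it extends above the Grade 4 limit |
| Thrombocytopenia | Grade 3 or 4 | <25,000 | Grade 3: <50,000; Grade 4: <25,000 | No |

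Only the platelet line pairs a two-grade label with a one-grade number. The line for other Grade 4 events does not recover counts of 25,000 to <50,000.

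**2. Which events fall in the gap.** These are related counts of 25,000 to <50,000 that last more than 7 days, require transfusion, or come with Grade 2 bleeding. Related bleeding of Grade 3 or higher is arguably a DLT under either reading, because criterion 1 of Section 5.3 counts any Grade 3 or higher non-hematologic event. Section 11.4.6.1 also asks for bleeds that need red-cell transfusion to be reported as Grade 3 or higher.

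**3. Effect of one such subject.** The stated limit is an incidence below 33.3%. It reproduces: 1/6 = 16.7% and 2/9 = 22.2% pass; 3/9 = 33.3% and 3/6 = 50% fail. One added DLT has these effects in Cohort 1:

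- 1/6 (accept) becomes 2/6 (add three subjects).
- 2/6 (add three) becomes 3/6 (de-escalate).
- 2/9 (accept) becomes 3/9 (de-escalate).

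**4. Average effect.** Let p be the DLT rate under the number, and q the added rate of events that only the label counts. Subjects are taken as independent. The chance that a dose is accepted is

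A(p) = (1−p)^6 + 6p(1−p)^5 + 15p²(1−p)^4 × (1−p)^3.

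The label never accepts a dose that the number rejects. So A(p) − A(p+q) is the chance that the two final decisions differ. For p = 0.20 and q = 0.02:

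- A(0.20) = 0.2621 + 0.3932 + 0.2458 × 0.512 = 0.781
- A(0.22) = 0.2252 + 0.3811 + 0.2687 × 0.4746 = 0.734
- Difference = 0.047

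| Assumed q | At least one such event in 6 subjects, 1−(1−q)^6 | Decisions differ, p = 0.10 (A = 0.957) | Decisions differ, p = 0.20 (A = 0.781) |
|---|---|---|---|
| 0.5% | 3.0% | 0.6 points | 1.2 points |
| 1% | 5.9% | 1.2 points | 2.3 points |
| 2% | 11.4% | 2.5 points | 4.7 points |

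Both p and q are assumptions. The documents give no rate for the disputed event.

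**The case against.** The strongest reply is that the parenthesis narrows the label on purpose. The same number stands in all three places. Inclusion criterion 6 admits subjects just above 50,000/mm³, and lower with marrow involvement. Under a <50,000 rule, a subject who enters at 51,000 and sits at 48,000 for eight days would count as a DLT and discontinue, provided the event is judged related. Section 5.6.1.4 would not modify ibrutinib for that platelet count without bleeding. A deliberate <25,000 limit is therefore plausible. What stands is that intent is unresolved; the repetition may be copying. But if <25,000 was meant, the mention of Grade 3 has no content and the label is what needs correcting.

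A second reply is that the Dose Level Review Committee would sort it out: CTCAE 4.03 governs, the list is only illustrative, and safety and statistics staff sit on the committee. This makes an oversight less likely. It does not make the count reproducible, and it leaves no record of the rule that was used.

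A third reply is that the effect is small and Phase 1b appears finished. Both parts are fair. They limit the size of the point and shape the remedy, but they do not remove the contradiction.

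**Conclusion.** The criterion contradicts itself as written, and the inconsistency can be shown from the protocol alone. It can decide Cohort 1 only if a gap event occurs alongside one or two other DLTs. The average effect is probably small: 0.6 to 4.7 percentage points over the assumed ranges above. It concerns Phase 1b dose selection, not the Phase 2 ORR test.

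A reader might infer three stronger conclusions that the documents do not support:

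- **That <25,000 is the mistake.** CTCAE 4.03 and the neutropenia line favour <50,000, but they do not prove it over relabelling the criterion as Grade 4. Likewise, the number reading misses DLTs, and so leans toward the higher dose, only if the label was intended.
- **That the effect is large.** Section 1.3.3.1 reports Grade 3 or 4 thrombocytopenia in 6.2% of pooled ibrutinib monotherapy subjects and 5.6% in the randomized CLL/SLL study. Using 6.2% as q would give 9.5 and 15.3 points. That overstates the extra rate: 6.2% includes Grade 4 events that the number can already count, and it is not limited to one cycle, to related events, or to the three qualifiers. The combination could differ from ibrutinib alone, but Section 1.4.3 does not list thrombocytopenia among the common or higher-grade events with MEDI4736 monotherapy.
- **That the RP2D was wrongly chosen.** The documents do not report any subject in the gap or say which threshold was applied.

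**What to change.** First, establish which threshold was used. Phase 1b appears complete: Phase 2 enrolment starts only once the RP2D is defined (SAP Section 1.1), and SAP Section 5 describes holding enrolment for the Phase 2 interim analysis. Rewriting the threshold without saying what was done could misdescribe how the dose was chosen. The SAP should therefore:

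- state the threshold actually applied;
- list any Phase 1b subject, including any replaced, with a qualifying count of 25,000 to <50,000;
- report whether counting those subjects would change the RP2D decision.

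Then make label and number agree in Section 5.3, the synopsis and SAP Section 1.1. The better-supported wording keeps Grade 3 or 4 and changes the number to <50,000/mm³. If <25,000 was intended, keep the number and change the label to Grade 4. A clause requiring worsening from baseline, for subjects who enter below 50,000 with marrow involvement, is optional, because Section 11.1.1 already excludes unchanged pre-existing conditions.

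The cost is one number or label in three places, a short SAP statement and a listing. The downside is that one more DLT might be counted, giving a slightly less favourable RP2D determination.

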5.4 Replacement of Subjects

During the Phase 1b DLT observation period, subjects will be replaced for any of the following reasons:

- Missed \geq 5 consecutive doses of ibrutinib or missed 7 total doses (not due to DLT)
- Missed dose of MEDI4736 or received the MEDI4736 dose outside of the protocolallowed window (±2 days) (not due to DLT)
- Study drug discontinuation for any reason other than DLT

Subjects who are replaced for missed doses may continue to receive study treatment if there is a clinical benefit, but they will not be part of the DLT analysis.

During the Phase 2 portion of the study, if a subject discontinues study drug prior to the first tumor response assessment for reasons other than progressive disease, the subject may be replaced.

5.5 Study Treatment

All eligible subjects will be treated with ibrutinib PO and MEDI4736 IV in 28-day cycles. Prior to the first cycle, ibrutinib will be given daily for 7 days in the ibrutinib lead-in period prior to starting MEDI4736. On infusion days where pharmacokinetic, pharmacodynamic, or biomarker samples are drawn post-dose, MEDI4736 IV should be given first, with administration of ibrutinib as soon as possible after the end of infusion.

Missed doses of ibrutinib and MEDI4736 will not be made up. Dose modification of MEDI4736 will not be permitted.

Dosing of ibrutinib will continue up to 3 years as long as the subject is deriving clinical benefit (CR, PR, or SD) and the subject is not experiencing unacceptable toxicity. Dosing of MEDI4736 will continue for a total of 12 cycles of therapy if clinical benefit is seen without safety concerns. Toxicity may result in discontinuation or hold of one study drug while the other may continue to be dosed. Depending on the suspected relatedness to either agent (or both), the Investigator may perform dose modification and/or dose delays as per Section 5.6.1.4 and/or Section 5.6.2.5 at his or her clinical discretion. Re-treatment with MEDI4736 will not be allowed following completion of 12 cycles of treatment, regardless of any dose delays, missed doses, or following permanent discontinuation for any reason.

5.5.1 Phase 1b

Two dose levels of ibrutinib (560 or 420 mg/day) and 2 dose levels of MEDI4736 (10 or 3 mg/kg IV every other week) may be tested. The starting dose will be 560 mg ibrutinib PO daily and MEDI4736 10 mg/kg IV every 2 weeks. Prior to the first cycle, there will be an ibrutinib lead-in period in which ibrutinib will be given for 7 days prior to starting MEDI4736.

The first subject in each dose cohort will be dosed as a sentinel subject with at least a 3-day observation period until the next subject in the cohort is dosed to monitor for any unexpected acute or overlapping toxicities.

Dose escalation of any agent (ibrutinib or MEDI4736) beyond the original assigned dose at any time will not be allowed.

5.5.2 Phase 2

Subjects will be administered ibrutinib in combination with MEDI4736 at the RP2D determined during the Phase 1b portion of the study. Prior to the first cycle, there will be an ibrutinib lead-in period in which ibrutinib will be given for 7 days prior to starting MEDI4736.

5.6 Study Medication

5.6.1 Ibrutinib

5.6.1.1. Formulation/Packaging/Storage

Ibrutinib capsules are provided as a hard gelatin capsule containing 140 mg of ibrutinib. All formulation excipients are compendial and are commonly used in oral formulations. Refer to the ibrutinib Investigator's Brochure for a list of excipients.

The ibrutinib capsules will be packaged in opaque high-density polyethylene plastic bottles with labels bearing the appropriate label text as required by governing regulatory agencies. Study drug will be dispensed in child-resistant packaging.

Refer to the Pharmacy Manual/site investigational product manual for additional guidance on study drug storage, preparation and handling.

Study drug labels will contain information to meet the applicable regulatory requirements.

5.6.1.2. Dose and Administration

Ibrutinib 560 mg (4 x 140-mg capsules) or 420 mg (3 x 140-mg capsules) is administered orally once daily. The capsules are to be taken around the same time each day with 8 ounces (approximately 240 mL) of water. The capsules should be swallowed intact and subjects should not attempt to open capsules or dissolve them in water. The use of strong CYP3A inhibitors/ inducers and grapefruit and Seville oranges should be avoided for the duration of the study (Appendix 4).

If a dose is not taken at the scheduled time, it can be taken as soon as possible on the same day with a return to the normal schedule the following day. The subject should not take extra capsules to make up the missed dose.

The first dose of ibrutinib will be administered in the clinic on Day 1, after which subsequent dosing is typically on an outpatient basis unless otherwise specified in Section 8 and Appendix 1. Ibrutinib will be dispensed to subjects in bottles at appropriate visits. When new study drug is dispensed, unused ibrutinib dispensed during previous visits must be returned to the site and drug accountability records (Section 12.8) should be updated. Returned capsules must not be redispensed to anyone.

5.6.1.3. Overdose

Any dose of study drug in excess of that specified in this protocol is considered to be an overdose. Signs and symptoms of an overdose that meet any SAE criterion must be reported as a SAE in the appropriate time frame and documented as clinical sequelae to an overdose. There is no specific antidote for ibrutinib. In the event of an overdose, subjects should be closely monitored and given appropriate supportive treatment.

Refer to Section 11 for further information regarding AE reporting.

5.6.1.4. Dose Modification for Adverse Reactions

For an ibrutinib-related adverse reaction, the dose of ibrutinib should be modified according to the dose modification guidelines in Table 3 if any of the following toxicities occur:

- Grade 4 neutropenia (ANC $<500/\mu$ L) for more than 7 days. See Section 6.1 and 6.3 for instructions regarding the use of growth factor support.
- Grade 3 thrombocytopenia (platelet count <50,000/mm³ (50 x 10⁹/L) in the presence of grade 2 or greater bleeding events.

- Grade 4 thrombocytopenia (platelet count $<25,000/\text{mm}^3$ (25 x $10^9/\text{L}$).
- Grade 3 or 4 nausea, vomiting, or diarrhea if persistent, despite optimal anti-emetic and/or anti-diarrheal therapy.
- Any other Grade 4 or unmanageable Grade 3 toxicity.

For Grade 3 or 4 atrial fibrillation or persistent atrial fibrillation of any grade, consider the risks and benefits of ibrutinib treatment. If clinically indicated, the use of anti-coagulants or anti-platelet agents may be considered for the thromboprophylaxis of atrial fibrillation (Section 6.2.3).

 Table 3.
 Ibrutinib Dose Modifications

Occurrence	Action to be Taken
First	Withhold study drug until recovery to Grade ≤ 1 or baseline; may restart at original dose level
Second	Withhold study drug until recovery to Grade ≤1 or baseline; may restart at 1 dose level lower (ie, 420 mg/day for original 560 mg/day dose; 280 mg/day for original 420 mg/day dose)
Third	Withhold study drug until recovery to Grade ≤1 or baseline; may restart at 1 dose level lower (ie, 280 mg/day for original 560 mg/day dose) or discontinue for original 420 mg/day dose
Fourth	Discontinue study drug

After a dose reduction, dose escalations of ibrutinib to the previous higher dose may be considered after consultation with the Medical Monitor if the event does not recur after at least one cycle of the lower dose.

If tumor lysis syndrome is diagnosed, follow the institutional guidelines for management.

Study treatment should be discontinued in the event of an ibrutinib toxicity lasting more than 28 days, unless reviewed and approved by the Medical Monitor.

Study treatment interruptions, dose reductions or modifications, or any other changes in study drug administration should be recorded in the clinical database.

5.6.2 MEDI4736

5.6.2.1. Formulation/Packaging/Storage

Liquid Drug Product

MEDI4736 is formulated at 50 mg/mL in 26 mM histidine/histidine-HCl, 275 mM trehalose dihydrate, 0.02% (w/v) polysorbate 80, pH 6.0. The investigational product is supplied as a vialed liquid solution in clear 10R glass vials closed with an elastomeric stopper and a flip-off

cap overseal. Each vial contains 500 mg (nominal) of active investigational product at a concentration of 50 mg/mL. The solution will be diluted with 0.9% saline for IV infusion.

Unopened vials of MEDI4736 liquid Drug Product must be stored at 2°C to 8°C (36°F to 46°F).

Refer to the Pharmacy Manual/site investigational product manual for additional guidance on study drug storage, preparation and handling.

Study drug labels will contain information to meet the applicable regulatory requirements.

5.6.2.2. Dose and Administration

The liquid product is to be diluted with 0.9% saline for IV infusion.

The first dose will be administered in the clinic on Cycle 1 Day 1 and then every 2 weeks thereafter.

MEDI4736 will be administered as an IV infusion approximately 1 hour in duration.

Following preparation of MEDI4736, the entire contents of the IV bag should be administered as an IV infusion over approximately 60 minutes (\pm 5 minutes), using a 0.2-µm in-line filter. The IV line should be flushed with a volume of normal saline equal to the priming volume of the infusion set used after the contents of the IV bag are fully administered, or complete the infusion according to institutional policy to ensure the full dose is administered and document if the line was not flushed. Since the compatibility of MEDI4736 with other IV medications and solutions, other than normal saline (0.9% [weight/volume] sodium chloride for injection), is not known, the MEDI4736 solution should not be infused through an IV line in which other solutions or medications are being administered.

Subjects will be monitored during and after the infusion with assessment of vital signs at the times specified in the Schedule of Assessments (see Appendix 1). In the event of a Grade ≤ 2 infusion-related reaction, the infusion rate of study drug may be decreased by 50% or interrupted until resolution of the event (up to 4 hours) and re-initiated at 50% of the initial rate until completion of the infusion. For subjects with a Grade ≤ 2 infusion-related reaction, subsequent infusions may be administered at 50% of the initial rate (see Table 4 for toxicity management). Acetaminophen and/or an antihistamine (eg, diphenhydramine) or premedication per institutional standard may be administered at the discretion of the investigator. If the infusion-related reaction is Grade ≥ 3 in severity, study drug will be discontinued.

As with any antibody, allergic reactions to dose administration are possible. Appropriate drugs and medical equipment to treat acute anaphylactic reactions must be immediately available, and study personnel must be trained to recognize and treat anaphylaxis. The study site must have immediate access to emergency resuscitation teams and equipment in addition to the ability to admit subjects to an intensive care unit if necessary.

